### **Study Termination:**

Patients who either complete the Study or terminate the Study early will have an End of Study (EOS) visit within 7 days ( $\pm$  2 days) of their last completed study visit. Clinical laboratory assessments, physical examination, vital signs, ECG, [REDACTED] [REDACTED] will be performed according to the Schedule of Events, Appendix 14.1. Blood samples for PK (cysteamine) and PD

(WBC cystine) will be collected 0.5 hour post RP103 dose administered at the clinic. For patients who have transitioned back to Cystagon®, PK and PD samples will be collected immediately prior to their next Cystagon® dose. Adverse events and concomitant medications will be collected.

### **Other Study Procedures:**

Females of child-bearing potential will provide a menstrual cycle history and be administered a serum pregnancy test at Screening (new patients only), and at each scheduled study visit. Height, weight, BMI and BSA determination will be performed at each visit according to the Schedule of Events.

### **6.2. Randomization**

Patients will not be randomized.

### **6.3. Duration**

Patients will be followed until Study termination; which can occur by patient, physician or Sponsor request, or until the RP103 drug is available through the appropriate marketing approval, or until the Sponsor terminates development of RP103 for this indication for any reason. Approximate treatment time in the Study is 96 months. However, a subject may withdraw consent or be withdrawn from the study prior to completion.

## **7. Selection of Subjects**

### **7.1. Inclusion Criteria**

The following criteria must be met by all subjects considered for Study participation.

7.1.1 Male and female subjects must have completed the last visit of Study RP103-03 and be willing to continue on RP103 treatment.

OR for patients who did not complete the RP103-03 study:

- 7.1.2 Male and female subjects with a documented diagnosis of cystinosis.
- 7.1.3 Subjects must be on a stable dose of Cystagon® at least 21 days prior to Screening.
- 7.1.4 [ no longer applicable ]
- 7.1.5 Within the last 6 months, no clinically significant change from normal in liver function tests [i.e., 1.5 times ULN for ALT and AST, and/or 1.5 times ULN for total bilirubin] and renal function [i.e., estimated GFR (corrected for body surface area)] at Screening as determined by the Investigator.
- 7.1.6 Subjects must have an estimated GFR (corrected for body surface area) > 30 mL/minute/1.73 m^2.

---

- 7.1.7 Sexually active female subjects of childbearing potential (i.e., not surgically sterile [tubal ligation, hysterectomy, or bilateral oophorectomy] or at least 2 years naturally postmenopausal) must agree to utilize the same acceptable form of contraception from Screening through completion of the Study. The acceptable forms of contraception for this Study include hormonal contraceptives (oral, implant, transdermal patch, or injection) at a stable dose for at least 3 months prior to Screening, barrier (spermicidal condom, diaphragm with spermicide), IUD, or a partner who has been vasectomized for at least 6 months. For pre-pubescent children, a documented attestation of abstinence from their parent or guardian will be acceptable.
- 7.1.8 Subject must be willing and able to comply with the Study restrictions and requirements.
- 7.1.9 Subject or their parent or guardian must provide written informed consent and assent (where applicable) prior to participation in the Study.

## **7.2. Exclusion Criteria**

- 7.2.1 Patients enrolled in the previous Study RP103-03 who did not complete their last scheduled study visit or who do not wish to continue on treatment with RP103.

AND for patients who did not complete the RP103-03 study:

- 7.2.2 Subjects less than 1 year old.
- 7.2.3 Subjects with current history of the following conditions or any other health issues that make it, in the opinion of the Investigator, unsafe for them to participate:
  - Inflammatory bowel disease (if currently active) or prior resection of small intestine;
  - Heart disease (e.g., myocardial infarction, heart failure, unstable arrhythmias, or poorly controlled hypertension) 90 days prior to Screening;
  - Active bleeding disorder 90 days prior to Screening;
  - History of malignant disease within the last 2 years.
- 7.2.4 Subject with a hemoglobin level of < 10 g/dL at Screening or, in the opinion of the Investigator, a hemoglobin level that would make it unsafe for the subject to participate.
- 7.2.5 [ no longer applicable ]
- 7.2.6 Subjects with known hypersensitivity to cysteamine and penicillamine.
- 7.2.7 Female subjects who are nursing, planning a pregnancy, known or suspected to be pregnant, or with a positive serum pregnancy screen.
- 7.2.8 Subjects who, in the opinion of the Investigator, are not able or willing to comply with the protocol.

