#### 4.2.6. Study RP103-HLTA-009

### 4.3. Risk/Benefits

Cystagon® (cysteamine bitartrate) is a cystine-depleting agent that is the only cystinosis treatment approved by FDA. Cystagon® is indicated for the management of nephropathic cystinosis in children and adults. Cystagon® is contraindicated in patients who have developed hypersensitivity to it or to cysteamine or penicillamine (Cystagon® Package Insert, 2007).

The most common adverse events (> 5%) associated with cysteamine were vomiting 35%, anorexia 31%, fever 22%, diarrhea 16%, lethargy 11%, and rash 7% (Cystagon® Package Insert, 2007). Less common adverse events associated with cysteamine include: CNS symptoms such as seizures, dizziness, lethargy, somnolence, depression, and encephalopathy; gastrointestinal tract symptoms including nausea, vomiting, anorexia and abdominal pain, sometimes severe. In addition, gastrointestinal ulceration and bleeding have been reported in patients on cysteamine therapy. Cysteamine has occasionally been associated with reversible leucopenia, abnormal liver function studies, skin lesions, headache, tinnitus, diplopia, blurry vision, loss of vision, pain behind the eye or pain with eye movement (Cystagon® Package Insert, 2007).

Patient adherence with Cystagon® is challenging due to significant adverse effects, dosing frequency, and the need for life-long treatment from the age of diagnosis. Since Cystagon® must be taken Q6H around the clock; patients must be awakened in the middle of the night to take their medication in order to maintain adequate white blood

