## **7.3. Removal of Subjects from Study Participation**

Subjects will be informed that they are free to withdraw from the Study at any time and for any reason. The Investigator may remove a subject from the Study if, in the Investigator's opinion, it is not in the best interest of the subject to continue the Study. Subjects may be discontinued due to the following: change in compliance with inclusion/exclusion criteria(ion) that is(are) clinically relevant and affects subject safety, occurrence of AEs that result in the subject or the Investigator requesting a Study withdrawal, occurrence of pregnancy, intake of non-permitted concomitant medication that might affect subject safety or Study assessments/objectives, etc.

Notification of discontinuation will immediately be made to the Sponsor's representative(s). In case of premature discontinuation of Study participation, efforts will be made to have the subject return to the clinic for a follow-up visit within  $7 \pm 2$  days of last study drug administration and perform all Follow-up/Study termination assessments [see Schedule of Events (Appendix 14.1)]. The date the subject is withdrawn from the Study and the reason for discontinuation will be recorded on the subject's CRF. All dropouts will be followed until resolution of any AEs or until the unresolved AEs are judged by the Investigator to have stabilized. For subjects who are discontinued by the Investigator or who voluntarily withdraw prematurely from the Study, replacement subjects may be enrolled at the discretion of the Sponsor.

Subjects may be withdrawn from the Study for the following reasons:

- Illness that prevents further administration of treatment;
- Unacceptable adverse event(s);
- Subject decides to withdraw from the Study;
- General or specific changes in the subject's condition render further treatment unacceptable for the Subject in the judgment of the Investigator;
- Protocol non-compliance;
- Cancellation of drug development;
- Request from IRB, Ethics Committee or regulatory agency.

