## 8. Treatment of Subjects

### 8.1. Study Treatment

The Sponsor, or designee, will provide the Investigator with adequate quantities of the RP103. The active ingredient in RP103 is cysteamine bitartrate; dosage is expressed as mg of cysteamine free base (see Table 8).

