### **11.7. Deviation Reporting**

The following protocol deviations will be recorded and summarized in the final report: 1) eligibility (inclusion/exclusion) violations, 2) study drug dosing violations, 3) excluded medication violations, 4) procedures performed outside the protocol-specified window, 5) procedures not done, 6) subject non-compliance and 7) other, to be specified by the Investigator.

All protocol deviations will be presented in a data listing.

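### Exclusion 7.2.6 joins cysteamine and penicillamine with 'and' where the contraindication in Section 4.3 has 'or': a minor wording error in an operative safety criterion

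*Protocol*

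**What the plan says.** Protocol 7.2.6 excludes "Subjects with known hypersensitivity to cysteamine and penicillamine". Exclusion criterion 6 in the synopsis (Section 3) has the same wording. In both places the criterion sits in the block for patients who did not complete RP103-03, so it governs new entrants and not those rolling over.

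Protocol 4.3 restates the label position for the marketed product: Cystagon is "contraindicated in patients who have developed hypersensitivity to it or to cysteamine or penicillamine". That section identifies Cystagon as cysteamine bitartrate, and Protocol 8.1 says "The active ingredient in RP103 is cysteamine bitartrate".

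No other inclusion or exclusion criterion names hypersensitivity. Three other provisions bear on the same patients:

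- 7.1.3, for new entrants: "Subjects must be on a stable dose of Cystagon® at least 21 days prior to Screening".
- 7.2.3, which excludes listed conditions or "any other health issues that make it, in the opinion of the Investigator, unsafe for them to participate".
- 7.3, under which the Investigator may remove a subject where, in the Investigator's opinion, "it is not in the best interest of the subject to continue the Study".

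**The concern.** A safety exclusion should carry over the contraindication that the protocol itself cites for the same substance. Section 4.3 makes hypersensitivity to either drug sufficient. Taken word for word, 7.2.6 requires both. A new entrant with known hypersensitivity to penicillamine alone, or to cysteamine alone, would then not be excluded by the one criterion that names the problem, and the decision would rest on the Investigator's judgement.

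The wording also affects how such an entrant is recorded. Protocol 11.7 begins: "The following protocol deviations will be recorded and summarized in the final report: 1) eligibility (inclusion/exclusion) violations". SAP 3.2 treats failure of any inclusion or exclusion criterion as a protocol violation. Whether a single-drug-hypersensitive entrant counts as a violation therefore depends on how one conjunction is read.

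**Working it through.** No arithmetic applies. The check is a comparison of texts.

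1. **Is the mismatch real?** Yes. 7.2.6 and synopsis criterion 6 both have 'and', so this is not a slip in one place or a fault in text extraction. Section 4.3 has 'or'. Cystagon and RP103 share the active ingredient (4.3 and 8.1), so the contraindication is relevant to the study drug.

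2. **What follows from each wording?** With 'and' taken as a strict conjunction, only a patient hypersensitive to both drugs is excluded. With 'or', a patient hypersensitive to either is excluded. The two wordings differ for the patient hypersensitive to cysteamine only and for the patient hypersensitive to penicillamine only.

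3. **Which reading was probably meant?**
   - Within 7.2, the other criteria that state alternatives (7.2.1, 7.2.3, 7.2.4, 7.2.7, 7.2.8) use 'or'. An example is 7.2.7: "Female subjects who are nursing, planning a pregnancy, known or suspected to be pregnant, or with a positive serum pregnancy screen". Taken alone, this makes the 'and' in 7.2.6 stand out.
   - The inclusion list in 7.1 uses 'and' to mean each of the items named. 7.1.1 and 7.1.2 admit male and female subjects, which as a strict conjunction nobody could satisfy. 7.1.5 gives one multiple of the upper limit of normal for ALT and AST, which is naturally a limit on each enzyme.
   - 7.2.6 has the form of 7.1.5: one condition with two objects. The 'or' criteria mostly join separate conditions.
   - The strict reading would also admit a patient known to be hypersensitive to the study drug's own active substance, which is implausible as an intention.

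   On balance 'either' is the likely intent. The words still do not say so.

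4. **Who could pass through under the literal wording?** Only a new entrant, and every new entrant must meet 7.1.3. A patient hypersensitive to cysteamine is unlikely to be on a stable Cystagon dose. A patient hypersensitive to penicillamine alone is also unlikely, because by Section 4.3 Cystagon is itself contraindicated for that patient. What remains is a patient prescribed Cystagon despite the contraindication. That patient is already taking the same active substance at a stable dose.

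5. **What else would catch such a patient?** 7.2.3 at entry and 7.3 afterwards, both at the Investigator's discretion. In addition, 10.1.1 stops an individual's dosing after a treatment-emergent event of CTCAE grade 3 or higher that is not likely related to the underlying disease. That rule acts only once harm has occurred.

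6. **Does any analysis change?** No. SAP 3.1 defines the Safety Population by receipt of at least one RP103 dose and the PK/PD Population by having at least one measurement. SAP 3.2 excludes nobody from the safety analysis for a violation.

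**The case against.** The best case against raising this is that it is a proofreading note. The drafters write 'A and B' for 'A as well as B' elsewhere in the eligibility section, and no investigator would knowingly enrol a patient allergic to cysteamine on the ground that penicillamine allergy was absent. Label-compliant prescribing of Cystagon, which 7.1.3 presupposes, has already screened for both hypersensitivities. Discretionary exclusion, removal and the individual stopping criterion sit behind that. No consequence for patients or analyses is shown.

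Most of this stands. It makes 'either' the probable reading and the practical exposure very small. It does not make the wording correct. 7.1.3 tests current Cystagon use, not allergy history. The discretionary provisions do not replace a named contraindication, and the stopping criterion is not an entry check. A criterion applied at up to 10 sites should not need readers to infer its meaning from usage elsewhere.

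A reader might go further and infer that the protocol chose to admit patients hypersensitive to one of the drugs. The documents do not support that. Nothing gives a rationale for such a choice, and Section 4.3 points the other way.

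A reader might also try to size the gap by counting the combinations of hypersensitivity that the two wordings treat differently. Those are logical cases, not patients, and the documents give no frequency for any of them.

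**Conclusion.** The point holds as a minor wording error in an operative safety criterion. The literal text of 7.2.6 and of synopsis criterion 6 is narrower than the contraindication in Section 4.3 for the same active substance, although the intended meaning is probably the broader one.

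The number of patients affected is not given and may be zero. The judgement that exposure is very small assumes that Cystagon was prescribed in line with the contraindication in Section 4.3 and that 7.1.3 was enforced. The only reporting consequence is whether a hypothetical entrant hypersensitive to one drug is recorded as an eligibility violation. A reader might infer that the safety or PK/PD results are affected. They are not, because neither analysis population in SAP 3.1 depends on this criterion.

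**What to change.** Replace 'and' with 'or' in Protocol 7.2.6 and in synopsis exclusion criterion 6, so that each refers to known hypersensitivity to cysteamine or penicillamine. Leave Section 4.3 as it is.

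The cost is one word in two places, with no change to visits, data collection, populations or analyses. SAP 1.1 is written partly as though enrolment has already taken place. If so, the same reading should be applied when eligibility violations are classified for the final report.

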## **7.3. Removal of Subjects from Study Participation**

Subjects will be informed that they are free to withdraw from the Study at any time and for any reason. The Investigator may remove a subject from the Study if, in the Investigator's opinion, it is not in the best interest of the subject to continue the Study. Subjects may be discontinued due to the following: change in compliance with inclusion/exclusion criteria(ion) that is(are) clinically relevant and affects subject safety, occurrence of AEs that result in the subject or the Investigator requesting a Study withdrawal, occurrence of pregnancy, intake of non-permitted concomitant medication that might affect subject safety or Study assessments/objectives, etc.

Notification of discontinuation will immediately be made to the Sponsor's representative(s). In case of premature discontinuation of Study participation, efforts will be made to have the subject return to the clinic for a follow-up visit within  $7 \pm 2$  days of last study drug administration and perform all Follow-up/Study termination assessments [see Schedule of Events (Appendix 14.1)]. The date the subject is withdrawn from the Study and the reason for discontinuation will be recorded on the subject's CRF. All dropouts will be followed until resolution of any AEs or until the unresolved AEs are judged by the Investigator to have stabilized. For subjects who are discontinued by the Investigator or who voluntarily withdraw prematurely from the Study, replacement subjects may be enrolled at the discretion of the Sponsor.

Subjects may be withdrawn from the Study for the following reasons:

- Illness that prevents further administration of treatment;
- Unacceptable adverse event(s);
- Subject decides to withdraw from the Study;
- General or specific changes in the subject's condition render further treatment unacceptable for the Subject in the judgment of the Investigator;
- Protocol non-compliance;
- Cancellation of drug development;
- Request from IRB, Ethics Committee or regulatory agency.

## 8. Treatment of Subjects

### 8.1. Study Treatment

The Sponsor, or designee, will provide the Investigator with adequate quantities of the RP103. The active ingredient in RP103 is cysteamine bitartrate; dosage is expressed as mg of cysteamine free base (see Table 8).

**Table 8: Study Drugs**

Study Drug	Cysteamine Bitartrate Delayed-release Capsules (RP103)
Form a	Capsules
Strength b	75 mg and 25 mg

[REDACTED] [REDACTED]  
a Specific ingredients/purity will be identified on the Certificate of Analysis (or equivalent) that is supplied for RP103.

b Provided strength is as cysteamine free base.

## 8.2. Identity of Investigational Products

The 25 mg strength Cysteamine Bitartrate Delayed-release Capsules (RP103, test product) are a size [REDACTED] [REDACTED] in white ink. They are provided in 60-count bottles.

The 75 mg strength Cysteamine Bitartrate Delayed-release Capsules [REDACTED] [REDACTED] in white ink. They are provided in 150-count bottles.

## 8.3. Storage of Investigational Products

Cysteamine Bitartrate Delayed-release Capsules (RP103) should be stored at the conditions specified in the current study pharmacy manual.

## 8.4. Concomitant Medications and Excluded Therapies

All patients will be asked about concomitant medications at study entry and at each study visit. For patients entering the Study on a chronic concomitant medication, adequate clarification of the reason for taking that medication must be documented in source documentation (e.g., medical history). Information about medications used during after study entry must also be recorded. Patients must observe the restrictions listed here for the specified time periods and throughout the study.

Patients entering the Study on Cystagon® will be asked to stop gastric acid reducing medications at least 12 hours before receiving their first dose of RP103 until Study termination. In cases of intolerable gastric upset, gastric acid reducing medications will be allowed, at the discretion of the Investigator. All gastric upset adverse events will be captured and recorded. All concomitant medications used to treat adverse events should be captured and recorded appropriately.

At Screening, the patient or parent will be provided with a daily diary to record protocol specified cysteamine medications, proton pump inhibitors (PPI) and other gastric acid reducing drugs, including over the counter gastric acid reducing medications, and instructed on its completion. At each clinic visit, the staff will review the diary for completion, collect completed diaries and re-dispense or issue a new one. Continued non-compliance with the diaries may be considered a reason for early Study termination. All diaries will be collected at Study completion.

---

Illegal or recreational alcohol or drug use is not allowed during the study. If the Investigator suspects illegal or recreational alcohol or drug use, alcohol or drug tests may be administered at the discretion of the Investigator.

### **8.5. Study Treatment Administration and Compliance**

All study treatments administered in the clinic will be under the supervision of clinic personnel. Patients not entering the trial from Study RP103-03 will be started on twice a day administration of RP103, where the total daily RP103 dose is 70% of their total daily stable Cystagon® dose.

If during the study any patient does not achieve a meaningful reduction of WBC cystine level (i.e., < 1 nmol ½ cystine/mg protein) or does not tolerate the dose, as determined by the Investigator, the patient may have their RP103 dose adjusted or may be terminated from the study.

A daily diary of cysteamine and gastric acid reducing medications will be maintained throughout the study.

## **9. Study Procedures**

Before any Study-specific procedures are performed, the patient and legal guardian (if appropriate) must receive an explanation of all Study procedures and must sign and date an Institutional Review Board (IRB) or Ethics Committee (EC)-approved written informed consent and assent (if applicable) form.

### **9.1. Schedule of Study Procedures**

#### **9.1.1. Screening**

For patients who completed Study RP103-03:

- The following data can be obtained from the RP103-03 Screening visit:
  - Demographics.
  - Medical history.
  - Medication history.
  - Menstrual history for females of childbearing potential.
- The following data can be obtained from the RP103-03 Termination visit:
  - Clinical laboratory
  - Physical examination
  - 12-lead ECG
  - Vital signs
- Dispense RP103 study medication.
- Schedule return clinic visit for Monthly Visit 1.

For patients who did not complete Study RP103-03:

- Review inclusion/exclusion criteria.
- Record demographics.
- Record medical history.
- Record medication history.
- Record menstrual history for females of childbearing potential.
- Perform a physical examination (see Section 9.10).
- Obtain clinical laboratory samples (serum chemistry, hematology, and urinalysis, see Section 9.7).
- Collect a cysteamine PK sample pre-dose RP103 administration. Actual collection time will be recorded.
- Collect a WBC cystine PD sample pre-dose RP103 administration (which should be 5-6 hours post last Cystagon® administration). Actual collection time will be recorded.
- Measure vital signs (blood pressure, heart rate, respiratory rate, and oral body temperature, see Section 9.11).
- Obtain a 12-lead ECG (see Section 9.9).
- Provide training for Daily Diary log of cysteamine and gastric acid reduction medications. Provide copy of daily medication diary.
- Schedule return clinic visits for Days 1, 4 and 5.

For all patients:

- Obtain serum pregnancy test from females of childbearing potential.
- Measure height and weight.
- Calculate BMI and BSA (see Appendix 14.5).
- [REDACTED]
- [REDACTED]
- [REDACTED]
- Prepare subjects for study participation by informing them of study restrictions and procedures.
- Provide copy of daily medications diary.
- Record concomitant medications.
- Monitor AEs.

For patients whose Screening visit was > 7 days prior to Day 1, complete the following prior to RP103 dosing:

- Re-assess inclusion/exclusion criteria.
- Record any changes since Screening to medical history, medication history, menstrual history for females of childbearing potential.
- Obtain serum pregnancy test from females of childbearing potential.
- Measure height and weight.
- Calculate BMI and BSA (see Appendix 14.5).
- Perform a physical examination (see Section 9.10).
- Collect a cysteamine PK sample pre-dose RP103 administration. Actual collection time will be recorded.
- Collect a WBC cystine PD sample pre-dose RP103 administration. Actual collection time will be recorded.
- Obtain clinical laboratory tests (serum chemistry, hematology, and urinalysis, see Section 9.7).
- Measure vital signs (blood pressure, heart rate, respiratory rate, and oral body temperature, see Section 9.11).
- Obtain a 12-lead ECG approximately 3 hours ( $\pm$  15 minutes) post RP103 administration (see Section 9.9).
- [REDACTED]
- [REDACTED]
- Record concomitant medications.
- Monitor AEs.

